12.2 Analysis Sets

12.2.1 Per-Protocol Analysis Set

The Per-Protocol analysis set (PPAS) will include all subjects who had no protocol deviations and will be defined for both stages as follows:

STAGE I:

The subjects who will be vaccinated but who meet any of the following study violations will be excluded from the PPAS in STAGE I:

- Subject did not meet all protocol-specified inclusion/exclusion criteria or definitive contraindications
- Subject did not receive the correct number of doses or injections
- Subject received a vaccine other than the one that he/she was randomized to receive
- Administration of vaccine at V05 was not done as per protocol (site and route of administration)

- Subject did not receive vaccine at V05 in the proper time window defined in the tables of the study procedures
- Subject did not provide a V06 post-dose serology sample in the proper time window
- Subject received a protocol-restricted medication, therapy, or vaccine in STAGE I as defined in Section 6.7.
- Subject's post-injection serology samples at V06 did not produce a valid test result (ie, a result different from "not-reportable" ['NR'] or missing, for at least one dengue serotype)

STAGE II:

The subjects who will be vaccinated but who meet any of the following study violations will be excluded from the PPAS in STAGE II:

- Subject did not meet all protocol-specified inclusion/exclusion criteria or definitive contraindications
- Subject did not receive the correct number of doses or injections
- Subject had negative serostatus at baseline dengue status.
- Subject received a vaccine other than the one that he/she was randomized to receive
- Administration of vaccine at V07 was not done as per protocol (site and route of administration)
- Subject did not receive vaccine at V07 in the proper time window defined in the tables of the study procedures
- Subject did not provide a V10 post-dose serology sample in the proper time window
- Subject received a protocol-restricted medication, therapy, or vaccine in STAGE II as defined in Section 6.7 of the protocol
- Subject's post-injection serology samples at V10 did not produce a valid test result (ie, a result different from "not-reportable" ['NR'] or missing, for at least one dengue serotype)
- Subjects randomized to Group 1 not included in the PPAS in STAGE I

12.2.2 Full Analysis Set

The FAS is defined as the subjects who received either at least one injection of CYD dengue vaccine or placebo and had at least one blood sample drawn and valid post-injection serology results (ie, a result different from "not-reportable" ['NR'] or missing, for at least one dengue serotype). Subjects will be analyzed by the vaccine group to which they were randomized.

12.2.3 Safety Analysis Set

The safety analysis set (SafAS) is defined as those subjects who have received either at least one injection of either CYD dengue vaccine or placebo^a. A SafAS is defined for each dose as the subset of subjects having received this dose; subjects will be analyzed according to the treatment received at this dose. For the analysis at any dose, subjects will be analyzed according to the treatment received at the first dose.

Safety data recorded for a vaccine received out of the protocol design will be excluded from the analysis (and listed separately).

12.2.4 Populations Used in Analyses

The PPAS will be used for the analysis for the primary objective. The FAS will be used for the superiority hypotheses testing for secondary objectives. All other immunogenicity analyses will be performed on the FAS.

The SafAS will be used for the description of clinical safety.

12.3 Handling of Missing Data and Outliers

12.3.1 Immunogenicity

For the computation of GMTs, a titer reported as < LLOQ will be converted to a value of 0.5 LLOQ.

For calculating titer ratio (GMTR), < LLOQ will be converted to 0.5 LLOQ for a numerator and < LLOQ will be converted to LLOQ for a denominator

Any titer reported as > upper limit of quantification (ULOQ) will be converted to ULOQ.

Missing data will not be imputed. No test or search for outliers will be performed.

12.3.2 Safety

No replacement will be done. Details will be described in the SAP.

12.4 Interim / Preliminary Analysis

No interim analyses are planned.

^a for which safety data are scheduled to be collected

12.5 Determination of Sample Size and Power Calculation

A total of 1050 subjects are planned to be enrolled with a 1:1:1 enrollment ratio (350 per group [or 1:1:1:1:1:1 randomization ratio, 175 per subgroup]) (Table S4). Considering a potential dropout rate of 15%, this sample size would provide 888 evaluable subjects.

Table 12.1: Power of the study based on the Primary Objectives - Stage I

Baseline Seropositive (%)	Population per group	Objectives	Endpoints	NI Margin	Power (%)
100%	296	Group 2 vs Group 1	28 days post-Inj 3 vs 28 days post-Inj 3	2	98.9
	296	Group 2 vs Group 1	1 year post-Inj 3 vs 1 year post-Inj	2	90.64
		Overall			88.6
90%	266	Group 2 vs Group 1	28 days post-Inj 3 vs 28 days post-Inj 3	2	97.86
	266	Group 2 vs Group 1	1 year post-Inj 3 vs 1 year post-Inj	2	88.52
		Overall			86.6
80%	235	Group 2 vs Group 1	28 days post-Inj 3 vs 28 days post-Inj 3	2	95.56
	235	Group 2 vs Group 1	1 year post-Inj 3 vs 1 year post-Inj	2	82.3
		Overall			78.64
70%	207	Group 2 vs Group 1	28 days post-Inj 3 vs 28 days post-Inj 3	2	92.06
	207	Group 2 vs Group 1	1 year post-Inj 3 vs 1 year post-Inj	2	74.52
		Overall			68.60
60%	178	Group 2 vs Group 1	28 days post-Inj 3 vs 28 days post-Inj 3	2	86.00
	178	Group 2 vs Group 1	1 year post-Inj 3 vs 1 year post-Inj	2	63.12
		Overall			54.28

Table 12.2: [REDACTED]

[REDACTED]	[REDACTED]	[REDACTED]	[REDACTED]	[REDACTED]	[REDACTED]
[REDACTED]	[REDACTED]	[REDACTED]	[REDACTED]	[REDACTED]	[REDACTED]
	[REDACTED]	[REDACTED]	[REDACTED]	[REDACTED]	[REDACTED]
	[REDACTED]	[REDACTED]	[REDACTED]	[REDACTED]	[REDACTED]
	[REDACTED]	[REDACTED]	[REDACTED]	[REDACTED]	[REDACTED]
[REDACTED]	[REDACTED]	[REDACTED]	[REDACTED]	[REDACTED]	[REDACTED]
	[REDACTED]	[REDACTED]	[REDACTED]	[REDACTED]	[REDACTED]
	[REDACTED]	[REDACTED]	[REDACTED]	[REDACTED]	[REDACTED]
	[REDACTED]	[REDACTED]	[REDACTED]	[REDACTED]	[REDACTED]
[REDACTED]	[REDACTED]	[REDACTED]	[REDACTED]	[REDACTED]	[REDACTED]
	[REDACTED]	[REDACTED]	[REDACTED]	[REDACTED]	[REDACTED]
	[REDACTED]	[REDACTED]	[REDACTED]	[REDACTED]	[REDACTED]
	[REDACTED]	[REDACTED]	[REDACTED]	[REDACTED]	[REDACTED]
[REDACTED]	[REDACTED]	[REDACTED]	[REDACTED]	[REDACTED]	[REDACTED]
	[REDACTED]	[REDACTED]	[REDACTED]	[REDACTED]	[REDACTED]
	[REDACTED]	[REDACTED]	[REDACTED]	[REDACTED]	[REDACTED]
	[REDACTED]	[REDACTED]	[REDACTED]	[REDACTED]	[REDACTED]

The following assumptions were considered:

- Alpha level of 2.5% (one sided) with a Bonferonni adjustment for multiplicity
- Non-inferiority margin of 2 ($\log_{10} = 0.301$)

†

- Dropout rate of 15%

The sample size will also provide a 95% probability of observing an AE that has a true incidence of $>0.85\%$ in each group ($N=350$).

For the measurement of the Cellular Immune Response, a convenience number of 60 subjects from a specific site in Colombia who consent to participate in additional immune response testing, the AIT subset, was selected, 10 subjects from each subgroup.

13 Ethical and Legal Issues and Investigator / Sponsor Responsibilities

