5.7 Changes in the Conduct of the Trial or Planned Analyses

The following parts written in SAP are the changes different from Protocol Amendment 1:

The definition of j had been clarified for the Overall hypothesis.

The definition of WHO criteria and the corresponding derivation method had been added for virologically-confirmed dengue cases.

Instead of presenting the number and percentage of subjects with hospitalized suspected dengue case, only the hospitalized virologically-confirmed dengue cases will be summarized.

The ANCOVA model will be tested in Year 1 (Group 2a and Group 3a vs. Group 1a) and Year 2 (Group 2b and Group 3b vs. Group 1b).

The definition of depleted and undepleted for Ab specificity had been added: undepleted is defined as BSA-control depleted sera and depleted is DENV depleted samples.

The definition of homotypic Abs had been changed based on recent research findings to a neutralizing antibody titer above 20 (1/dil) following DENV depletion. Heterotypic antibodies will not be analyzed.

Delete “If non-inferiority is not achieved in Primary Objective, assessments of immunogenicity will be descriptive.” The descriptive analyses will conduct anyway regardless of the non-inferiority is achieved or not.

The definition of successful conclusion at Stage I and Stage II separately was added for clarity. Bonferroni adjustment for multiple testing at 28 days and 1 year post-Inj3 between Group 2 and Group 1 was removed and the adjustment of power was added as illustrated in Section 5.5.

The age stratus (9-16, 17-45 and 46-50 years of age) were added in definition of age group.

The definition of AUC-MB was added.

Description and comparison of GM in seropositive subjects between age strata were added, both overall and within each Group. These will allow the assessment of immunogenicity profile by age strata.

The ANCOVA model was added for 28 days after injection 3 between age strata adjusting for baseline neutralizing Ab levels.

The ANCOVA model was added for 28 days post-booster between age strata adjusting for the pre-booster neutralizing Ab levels.

6 References List

- 1 Newcombe R.G., Two-sided confidence intervals for the single proportion: comparison of seven methods, *Statistics in Medicine*, (1998) 17, 857-872

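### The Overall Stage I power of 88.6% in the protocol's 100%-seropositive row contradicts the two powers beside it; it should read 89.6% if those stand

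*Protocol*

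**What the plan says.** Protocol Section 12.5 sets out the design: "A total of 1050 subjects are planned to be enrolled with a 1:1:1 enrollment ratio". It continues: "Considering a potential dropout rate of 15%, this sample size would provide 888 evaluable subjects". That is 296 per group.

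Table 12.1, "Power of the study based on the Primary Objectives - Stage I", then covers five assumed baseline-seropositive percentages (100, 90, 80, 70 and 60%). Each row gives the power for Group 2 against Group 1 at 28 days, the same at 1 year, and an Overall power. The 100% row reads 98.9%, 90.64% and 88.6%. Table S4 in the synopsis (Planned Sample Size) prints the same figures. Neither place says how Overall is calculated.

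The listed assumptions include "Alpha level of 2.5% (one sided) with a Bonferonni adjustment for multiplicity" and "Non-inferiority margin of 2".

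The SAP later changes the Stage I multiplicity rule. Section 5.7 states: "Bonferroni adjustment for multiple testing at 28 days and 1 year post-Inj3 between Group 2 and Group 1 was removed". SAP Table 5.2 gives revised per-test powers (99.52% and 95.20% in the 100% row) and has no Overall row.

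**The concern.** Stage I has two primary non-inferiority objectives, one at 28 days and one at 1 year. The Overall figure is the only place where the protocol puts a number on the chance of meeting both. In the 100% row that number does not follow from the two powers it summarises, although the other rows follow one clear rule.

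Little is at stake for the design. What suffers is the reliability of a published planning table: a reader who checks one row and finds it inconsistent cannot tell whether the Overall figure or one of its components is at fault.

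**Working it through.** **Inputs.** All come from protocol Table 12.1: the 28-day power p1, the 1-year power p2 and the printed Overall.

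**Step 1. Identify the rule.** Try Overall = p1 × p2.

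| Seropositive (n per group) | p1 (%) | p2 (%) | p1 × p2 (%) | Printed Overall (%) | Product minus printed |
|---|---|---|---|---|---|
| 60% (178) | 86.00 | 63.12 | 54.28 | 54.28 | 0.00 |
| 70% (207) | 92.06 | 74.52 | 68.60 | 68.60 | 0.00 |
| 80% (235) | 95.56 | 82.3 | 78.65 | 78.64 | 0.01 |
| 90% (266) | 97.86 | 88.52 | 86.63 | 86.6 | 0.03 |
| 100% (296) | 98.9 | 90.64 | 89.64 | 88.6 | 1.04 |

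The product reproduces the plan's own figure in four rows. In the 100% row, 0.989 × 0.9064 = 0.8964.

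**Step 2. Ask whether any other rule could give 88.6%.** The probability that both tests succeed lies between p1 + p2 − 1 and the smaller of p1 and p2, whatever the dependence between them. For the 100% row:

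- lower limit: 98.9 + 90.64 − 100 = 89.54%
- upper limit: 90.64%

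Taking the components at the bottom of their rounding intervals (98.85 and 90.635) lowers the limit only to 89.485%. The printed 88.6% lies outside the possible range.

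**Step 3. Look at the component powers.** The 28-day column rises smoothly. The 1-year column rises by 11.40, 7.78, 6.22 and then 2.12 points over steps of 28 to 31 subjects per group, so the last step looks short. As a check, I modelled power as the product over four serotypes of Φ(c_i√n − z). This assumes independent serotypes and one-sided alpha 0.0125, that is, 2.5% split over two tests; the protocol does not give the divisor. The c_i are free because the standard deviations and assumed ratios are not visible.

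- Fitted to the other four rows, the model predicts 92.5% at n = 296. Variants that fit those rows well give about 92.4 to 92.8%.
- Fitted to all five rows, it gives 91.6% at n = 296 (0.9 above the printed value) and 87.7% at n = 266 (0.8 below the printed 88.52%).
- The SAP's 95.20% at alpha 0.025, converted to alpha 0.0125, gives 90.6 to 91.7%, depending on how many equally demanding serotypes are assumed (four down to one). Fitting the whole SAP 1-year column and converting gives about 91.8%.

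These values run from 90.6 to 92.8%. They do not settle whether 90.64% is wrong.

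**Step 4. Joint power implied by SAP Table 5.2, if the two tests were independent.**

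- 100%: 99.52 × 95.20 = 94.7%
- 90%: 98.94 × 93.26 = 92.3%
- 80%: 97.76 × 89.22 = 87.2%
- 70%: 95.78 × 83.54 = 80.0%
- 60%: 92.92 × 75.64 = 70.3%

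**The case against.** The strongest reply is that this is a one-digit slip with no consequence. The row is the ceiling case, whereas the synopsis expects 60 to 70% of enrolled subjects to be booster-eligible. The Overall figures at 60, 70 and 80% are right, and the 90% figure is right to rounding. The slip understates power, and the SAP has superseded these figures. All of that stands, and it is why the point is minor.

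A second reply is that the protocol never defines Overall as a product, so a departure from the product proves nothing. This does not stand: 88.6% is below the minimum under any dependence, so the definition does not matter.

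Three stronger readings are tempting, and the documents do not support them:

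- **That the 90.64% entry is also wrong.** The standard deviations and assumed ratios are blacked out. The fit that flags the entry uses four free parameters on four points and extrapolates beyond them. The converted SAP figures come close to the printed value, and part of the irregularity may lie in the 90% row.
- **That multiplying the powers is itself an error.** It is a common planning approximation. Both tests use largely the same subjects, so positive dependence is expected, and the product is then conservative.
- **That the SAP gives no probability of meeting both Stage I objectives.** Part of SAP Section 5.5 is redacted just before Table 5.2. Only the absence of an Overall row in that table can be seen.

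**Conclusion.** The Overall power in the 100% row is wrong as printed in both protocol tables. Given the row's own components it should be 89.64%, printed as 89.6%, so the figure is low by 1.04 points. That it is inconsistent needs no assumption beyond the printed powers. The corrected value assumes that both components stand and that Overall is the product, as in the other four rows.

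The effect is small: one best-case row, an error on the cautious side, no change to the 350 per group, and revised per-test powers in the SAP. The 1-year entry of 90.64% is irregular against its column and worth confirming, but no error in it has been shown.

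**What to change.** - Change Overall from 88.6% to 89.6% in the 100% row of protocol Table 12.1 and synopsis Table S4, provided that 98.9% and 90.64% are confirmed.
- Ask the sponsor to check the 1-year entry at n = 296 (90.64%) against the source power calculation. If it changes, recompute Overall from the new value.
- Optionally, add an Overall row to SAP Table 5.2 and say how it is calculated. Under independence it would read 94.7, 92.3, 87.2, 80.0 and 70.3%.

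The cost is one corrected number in two tables and one look-up. Sample size, analyses and conduct are unaffected.

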13.1 Ethical Conduct of the Trial / Good Clinical Practice

The conduct of this trial will be consistent with the standards established by the Declaration of Helsinki and compliant with the ICH guidelines for GCP as well as with all local and / or national regulations and directives.

13.2 Source Data and Source Documents

“Source data” are the data contained in source documents. Source documents are original documents or certified copies, and include, but are not limited to, DCs, MAs, medical and hospital records, screening logs, ICFs / AFs, telephone contact logs, and worksheets. The purpose of trial source documents is to document the existence of subjects and to substantiate the integrity of the trial data collected. Investigators must maintain source documents so that they are accurate, complete, legible, and up to date.

For missing or discrepant data on a DC, the study coordinator or designee will obtain verbal clarification from the subject, enter the response into the "Investigator's comment" page of the DC, and transfer the information to the eCRF.

The subject pre-screening log should list all individuals contacted by the Investigators to participate in the trial, regardless of the outcome.

The Investigator must print^a any electronic records on an ongoing basis, sign and date them immediately after creation, and keep the printouts on file as source documents that can be verified by the Sponsor or an inspector against the electronic records. Any later changes of an electronic record require the record to be re-printed, dated (with an indication of the date of change), and signed. Such records must also be kept together with the original printed copy.

13.3 Confidentiality of Data and Access to Subject Records

Prior to initiation of the trial, the Investigator will sign a fully executed confidentiality agreement with Sanofi Pasteur.

Sanofi Pasteur personnel (or designates), the IECs / IRBs, and regulatory agencies, including the FDA, require direct access to all study records, and will treat these documents in a confidential manner.

In the event a subject's medical records are not at the investigational site, it is the responsibility of the Investigator to obtain those records if needed.

13.4 Monitoring, Auditing, and Archiving

13.4.1 Monitoring

Before the start of the trial (ie, before the inclusion of the first subject in the first center the Investigators and the Sponsor's staff or a representative will meet at the site-initiation visit to discuss the trial protocol and the detailed trial procedures. Emphasis will be placed on inclusion and exclusion criteria, visit timing, safety procedures, informed consent procedures, SAE reporting procedures, eCRF completion, and the handling of samples and products. The Sponsor's staff or a representative will ensure and document that all material to be used during the trial has been received at the site; and that the study Investigator team and local Sponsor/delegate staff have been properly informed about the trial, GCP and regulatory requirements, and the Sponsor's procedures. Specific training sessions for the study Investigator team and the CRAs on these topics may be performed as necessary, and should be documented.

The following instruction manuals will be provided: the eCRF Completion Guidelines for entering data into the eCRF, and the Operating Guidelines for detailed trial procedures such as the product management and sample-handling procedures.

After the start of the trial, the Sponsor's staff or a representative will be in regular contact with the investigational team through telephone calls and regular follow-up visits. The Investigator or delegate must be available for these visits, and must allow the Sponsor/delegate staff direct access to subject medical files and CRFs. During these visits, the Sponsor/delegate staff will:

^a Unless the electronic medical records are managed by validated computerized systems that are compliant with US 21 CFR Part 11, in which case they are acceptable on their own.

- Evaluate the quality of the trial progress (adherence to protocol and any study-specific guidelines, quality of data collection and document completion, signature of consent forms, occurrence of SAEs, sample and product management, cold chain monitoring, archiving).
- Source-verify completed CRFs and any corresponding answered queries.
- Determine the number of complete or ongoing issues identified at monitoring visits (eg, protocol deviations, SAEs). Any identified problems will be discussed with the Investigator, and corrective or preventive actions will be determined, as appropriate.
- After all protocol procedures have been completed and the data have been entered into the eCRF, the Investigator must still be available to answer any queries forwarded by the Sponsor. All data-related queries must be completed prior to database lock.

At the end of the trial, a close-out visit will be performed to ensure that:

- The center has all the documents necessary for archiving
- All samples have been shipped to the appropriate laboratories
- All unused materials and products have been either destroyed or returned to the Sponsor

13.4.2 Audits and Inspections

A quality assurance audit may be performed at any time by the Sponsor's Clinical Quality Assessment (CQA) department or by independent auditors to verify that the trial has been conducted according to the protocol, GCP and ICH requirements, and other applicable regulations. An inspection may be conducted by regulatory authorities. The Investigator must allow direct access to trial documents during these inspections and audits.

13.4.3 Archiving

The Investigator must keep all trial documents after the completion or discontinuation of the trial, whatever the nature of the investigational center (private practice, hospital, or institution), for as long as required by applicable laws and regulations. In the absence of any applicable laws or regulations, trial documents will be kept at a minimum for the duration indicated on the Clinical Trial Agreement (CTA). In no event, should study personnel destroy or permit the destruction of any trial documents upon less than 90 days advance written notification to the Sponsor. In addition, trial documents should continue to be stored, at Sponsor's sole expense, in the event that the Sponsor requests in writing that such storage continues for a period of time that exceeds that required by any applicable law or regulation or the CTA. The Investigator will inform Sanofi Pasteur of any address change or if they will no longer be able to house the trial documents.

Archived data may be held on electronic records, provided that a back-up exists and that a hard copy can be obtained if required. The protocol, documentation, approvals, and all other documents related to the trial, including certificates attesting that satisfactory audit and inspection procedures have been carried out, will be kept by the Sponsor in the Trial Master File (TMF). Data on AEs are included in the TMF. All data and documents will be made available if requested by relevant authorities.

13.5 Financial Contract and Insurance Coverage

A CTA will be signed by all the parties involved in the trial's performance, if relevant. The Sponsor has an insurance policy to cover any liabilities that may arise from use of the product and / or the study protocol.

Specifically for the subjects identified as seronegative at baseline, Sanofi Pasteur will also cover reasonable expenses related to healthcare for dengue illness for 10 years after the last dose received. Details will be communicated to the Ethics Committees/Institutional Review boards and to study participants.

